however, are not universal and vary between patients and across surgical procedures. It is estimated that 20-30% of patients experience suboptimal weight loss or significant weight regain within the first few postoperative years. Reasons for this are not fully understood, but likely involve both physiological processes and behavioral factors (e.g., difficulty adhering to the dietary and physical activity recommendations made prior to surgery). Extreme Obesity More than one-third of American adults are obese, defined by a body mass index (BMI) of 30 kg/m2.1 Furthermore, 8.3% of women and 4.4% of men are extremely obese, defined by a BMI 40 kg/m2.1 Obesity, and extreme obesity in particular, is associated with major health complications including coronary heart disease, hypertension, type 2 diabetes mellitus, sleep apnea, and osteoarthritis.2-4 Surgical Treatment of Extreme Obesity Bariatric surgery is currently recommended for individuals 18 years and older with a BMI of 40 kg/m2 or those with a BMI of 35 kg/m2 in the presence of significant co-morbidities.5,6 Approximately 200,000 individuals are estimated to undergo bariatric surgery in the United States each year. The most common surgical procedures include the gastric bypass (GB), sleeve gastrectomy (SG), and adjustable gastric banding (AGB).7,8 As of 2013, the GB was the most common procedure in the United States, comprising 56% of all procedures; the SG comprised 36.3%.8 Anecdotal reports suggest that the SG is increasing in popularity while the AGB is now performed infrequently. With all three procedures, patients typically reach their maximum weight loss of 20-35% of body weight 12 months after surgery.3,4,9-16 These weight losses are associated with significant improvements in obesity-related co-morbidities and decreased risk of mortality.3,4,11,17-24 Despite these impressive results, studies have found that approximately 25% of patients who undergo bariatric surgery fail to reach or maintain the expected postoperative weight loss.25-27 Courcolous and colleagues, for example, observed that 23.6% of GB patients regained weight between postoperative year 1 and year 2. Less is known about the typical postoperative weight trajectory of patient who have undergone SG. Recent studies have suggested that weight regain is associated with deterioration of many of the health benefits seen with bariatric surgery.12,28-31 Psychosocial Status and Psychopathology in Candidates for Bariatric Surgery Extreme obesity is associated with a significant psychosocial burden, including impairments in quality of life, body image, sexual behavior and other areas of psychosocial functioning.32 While this distress is believed to contribute to the decision to have bariatric surgery, its impact on postoperative outcomes is less clear. At present, little is known about the physiological and behavioral contributions to success or failure of bariatric surgery.33 Regardless, weight regain after bariatric surgery is frequently attributed to preoperative psychosocial and behavioral factors.27,34-41 More specifically, there has been a great deal of interest in the presence of formal psychopathology in bariatric surgery patients and its potential contribution to postoperative outcomes.42-45 At least six studies have described rates of psychopathology in candidates for bariatric surgery using structured diagnostic instruments.46-51 Lifetime rates of any psychiatric diagnoses ranged from 36.8%-72.6%, higher than those reported in most studies of the general population. Mood disorders were the most frequent diagnoses, seen in 22.0%-54.8% of patients. Substance use disorders (SUDs) were found in up to 35.7% of patients and alcohol abuse or dependence in up to 33.2%. Binge eating disorder (BED), defined as eating an unusually large amount of food within a short period of time coupled with a loss of control over eating, has been diagnosed in 4.6% to 27.1% of patients. Current diagnoses (as compared with lifetime) were less common, reported in 20.9%-55.5% of candidates for surgery. Mood disorders were diagnosed in up to 31.5%. BED ranged from 3.4%-41.9%. Current substance use was seen in less than 2% of patients. (Note. The lower percentages of those with current psychopathology, as opposed to lifetime psychopathology, are expected.) While studies of the psychosocial characteristics of bariatric surgery candidates have been informative, they are not without limitations. Many studies have suffered from methodological concerns, including small sample sizes or lack of an appropriate comparison group. Further, establishing psychiatric diagnoses prior to bariatric surgery is challenging. Perioperative guidelines suggest that patients undergo an evaluation with a mental health professional prior to surgery3 and most third party payers require these evaluations. However, most programs do not use structured clinical interviews to establish diagnoses for clinical purposes.52,53 Several studies have suggested that candidates for bariatric surgery engage in impression management prior to surgery, in which they minimize reports of psychopathology to present themselves to the bariatric team in the most favorable light.54-56 To address this issue, assessment of psychiatric symptoms for research purposes is recommended to occur independently from the required clinical evaluation, as we will do in the proposed study. Nevertheless, studies focusing on the relationship between specific diagnoses and postoperative outcomes may fail to account for other psychological constructs that may be shared across diagnoses. Mood disorders, BED, and SUDs all share the common psychological construct of impulsivity, considered an important aspect of executive functioning. A lack of impulse control may contribute to the excessive weight gain seen in extreme obesity and may impact the results of bariatric surgery. Disinhibition and Impulsivity among Persons with Extreme Obesity Studies have suggested that individuals with obesity, and in particular those with extreme obesity presenting for bariatric surgery, show some deficits in executive functioning. For example, candidates for bariatric surgery have shown deficits in working memory, mental flexibility, motor speed and complex attention.57,58 These deficits could impact comprehension and retention of information presented to patients during the preoperative consultation process and, thus, negatively impact the ability to adhere to the dietary and behavioral changes required for an optimal postoperative outcome.45 At the same time, metabolic dysregulation, such as insulin resistance or hyperglycemeia seen in type 2 diabetes, also is associated with cognitive deficits, suggesting a potential physiological mechanism for the relationship.59-61 Dietary disinhibition, defined as a loss of control over eating, plays a central role in the overconsumption of food and, subsequently, the development of obesity.62.63 Disinhibition is similar to impulsivity, the term more commonly used in the substance use and smoking cessation literatures. Impulsivity is a multi-faceted construct and refers to the absence of the ability to inhibit an automatic behavior (otherwise known as response inhibition)64,65 and the tendency to discount future consequences in favor of more immediate outcomes (known as delay discounting).66,67 Similar to the role of disinhibition in obesity, impulsivity contributes to the development of and relapse with SUDs. Indeed, response inhibition and delay discounting are associated with both SUDs68-70 and obesity.71,72 Both also predict response to treatment for both SUDs73-75 and obesity.76 Chronic overeating and binge eating share several neurobiological and behavioral similarities with SUDs.77,78 In this regard, both may be viewed as behavioral disorders, in which intake (of food, alcohol, and/or drugs) escalates to a rate that is unhealthy and maladaptive. Nevertheless, the specific nature of the relationship between binge eating and substance use remains to be fully elucidated.79 There are similarities between binge eating and addictive disorders, including craving for the desired substance (drug or highly palatable food), a sense of loss of control when using, repeated attempts to control use despite clear adverse consequences, and the dedication of much time in obtaining and using the substance.80-82 Thus, the disinhibition observed with obesity and binge eating, the impulsivity seen with substance use disorders, and the emotional dysregulation associated with mood disorders all likely share commonalities (dashed lines in Figure 1) that may both contribute to the development of extreme obesity and also may be associated with weight loss (solid lines in Figure 1) and changes in psychosocial status after bariatric surgery. Psychosocial Status and Psychopathology after Bariatric Surgery In general, individuals who undergo bariatric surgery report dramatic improvements in psychosocial status and functioning postoperatively.83,84 The vast majority of patients report significant reductions in symptoms of depression and anxiety in the first postoperative year. They also report significant improvements in health and weight-related quality of life. Patients also report improvements in body image, sexual functioning, and relationship satisfaction.85-87 The relationship between preoperative psychopathology and postoperative outcomes is less robust.34,84 Livhits and colleagues reviewed this literature and concluded that the preoperative factors of BMI, BED, and the presence of personality disorders provided the strongest negative associations with postoperative weight loss.42 At least two studies have suggested that preoperative psychopathology, particularly mood and anxiety disorders, is associated with smaller weight postoperative weight losses.88,89 The relationship between BED and postoperative weight loss is unclear; some studies have found a relationship between preoperative BED and postoperative weight loss90.91 while others have not.92-94 Additionally, two studies have suggested that a history of substance abuse is associated with larger weight losses following bariatric surgery.95.96 The interpretation of this counterintuitive finding is that the selfregulation skills that help patients maintain their sobriety also help patients adhere to the demands of the recommended postoperative diet. Disinhibition and Impulsivity following Bariatric Surgery Encouragingly, studies have shown that there are improvements in executive functioning in persons with extreme obesity in the first two years after bariatric surgery.97,98 Postoperatively, patients typically report decreases in disinhibition and hunger, as well as increases in cognitive restraint.99,100 The physical aspects of bariatric surgery typically prevent individuals from eating the objectively large amount of food necessary to meet the diagnostic criteria of BED. However, many individuals continue to report the feeling of loss of control over their eating.44 The self-reported inability to control these impulses postoperatively is associated with smaller weight losses and greater emotional distress in the first few postoperative years.91,99,101,102 There is additional evidence that patients have difficulty with impulse control after surgery. A number of studies have suggested that there is an increased risk of substance abuse following bariatric surgery.101,103,104 King and colleagues,105 in their seminal investigation, found an increased rate of alcohol use disorder in the second postoperative year as compared to the year prior to surgery or in the first postoperative year. Other recent studies also have found increases in alcohol or composite substance abuse (drug, alcohol, or cigarettes) in the first two years after bariatric surgery.106-108 Postoperative substance use has been associated with smaller postoperative weight losses, postoperative nocturnal eating, and subjective hunger.109 Patients at

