
Characteristics of the Study Population

Target population

Adults aged 18-65 years old who plan to undergo one of two bariatric surgeries, either Rous-en-Y Gastric Bypass (RYGB) or Laparoscopic Sleeve Gastrectomy (LSG) at the University of Pennsylvania Health System. Based on our previous studies of bariatric surgery patients, we expect that approximately 80% of participants will be women and 20% of participants will be ethnic minorities.

Subjects enrolled by Penn Researchers 300

Subjects enrolled by Collaborating Researchers

0

Accrual

Participants will be recruited from the Bariatric Surgery Programs at the Hospital of the University of Pennsylvania and Presbyterian Medical Center, all part of Penn Medicine. We will enroll participants until a total of 300 adults have completed baseline visits. We anticipate that we will need to consent a larger number of participants in order to meet this enrollment goal. Based on our previous studies of bariatric surgery patients, we expect that approximately 80% of participants will be women and 20% of participants will be ethnic minorities. [name], Director of the Bariatric Surgery Program, conducts approximately 300 bariatric surgery operations per year. Additional surgeons in the Bariatric Surgery Program (at the Hospital of the University of Pennsylvania, Presbyterian Medical Center, and Pennsylvania Hospital) operate on approximately 200 patients per year. In order to increase the diversity and size of our sample, participants will also be recruited from the Temple Health Bariatric Surgery Program. The patient flow at Temple Health is similar to that of the Penn Health System (described below). Participants will be approached by the Research team during their pre-operative testing and education process.

Key inclusion criteria

We seek to enroll a sample of patients that is representative of those who present for bariatric surgery. We have based our exclusion criteria for the study largely on the clinical criteria used for bariatric surgery as well as our previous studies with bariatric patients. Inclusion Criteria: Adults aged 18-65 years old 18 years of age or above BMI of 35-60 kg/m2 (or 35 kg/m2 in the presence of significant weight-related comorbidities, including established coronary artery disease, established peripheral arterial disease, symptomatic carotid artery disease, sleep apnea, metabolic syndrome, cardiomyopathy, hypertension, and debilitating joint pain).

Key exclusion criteria

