
Discounting Task (DDT): participants choose between a smaller reward available immediately (e.g., \$20 today) and a larger reward available after a longer delay (e.g., \$40 in a month). People differ in their degree of delay discounting, the extent to which they forgo larger monetary magnitudes in the future in order to obtain immediate rewards. As in previous work, the immediate reward will be fixed and the magnitude and delay of the larger, later reward will vary from trial to trial. Participants will make 51 choices. The primary outcome will be the subjects discount rate, which will be estimated by fitting a logistic regression that assumes a persons decisions are a stochastic function of the difference in subjective value between the two options.127 Keeping with standard behavioral findings128,129 we will assume that subjective value (SV) is a hyperbolic function of the reward amount (A) and delay (D): SV = A/(1+kD), where k is the participants discount rate. Larger values of k indicate a greater degree of discounting future rewards. A composite measure of impulsivity will be calculated by averaging individual z-scores derived from the SST, Stroop interference score, and k-value. We predict that higher levels of impulsivity indicating poor response inhibition and greater discounting of future rewards (i.e., slower SST, higher Stroop interference score, and higher k-values) will be associated with less weight loss 24 months following bariatric surgery. Psychopathology: Psychopathology measures will be administered via interview or questionnaire at the following time points: baseline and 6, 12, and 24 months after surgery. The tasks are: Structured Clinical Interview for the DSM-5, Research Version (SCID-5-RV)129 is a semistructured interview for making DSM-5 diagnoses for mood, anxiety, eating, substance use, and psychotic disorders. A trained clinician or mental health professional who is familiar with the DSM-5 classification and diagnostic criteria administers the measure, which takes about 2.5 hours. Beck Depression Inventory-II (BDI-II)130: survey used to measure mood. It is the most widelyused measure of depressive symptomatology. Alcohol Use Disorders Identification Test (AUDIT)164: assesses the presence of alcohol use disorders before and after surgery. The Drinker Inventory of Consequences131 is a self-administered 50-item questionnaire designed to measure adverse consequences of alcohol use in five areas: Interpersonal, Physical, Social, Impulsive, and Intrapersonal. Each scale provides a lifetime and past 3-month measure of adverse consequences, and scales can be combined to assess total adverse consequences. The Fagerström Nicotine Tolerance Questionnaire132 is an 8-item, self-report designed to measure physical dependence to nicotine. Urine Drug Screens: collected in temperature sensing cups to ensure valid samples. Urines will be tested for common drugs of abuse (cocaine, opiates, amphetamines, methamphetamine, marijuana). A composite measure of psychopathology will be calculated by averaging individual z-scores derived from the presence/absence of DSM diagnoses, the BDI-II score, and the substance use measures. We predict that higher levels of psychopathology will be associated with less weight loss 24 months following bariatric surgery. Eating Behavior: Eating behavior measures will be administered via interview or questionnaire at the following time points: baseline and 6, 12, and 24 months after surgery. Total administration time is approximately 30 minutes. The tasks are: The Eating Inventory134: 51-item self-report inventory that measures three factors related to eating behavior: 1) cognitive restraint, 2) disinhibition, and 3) hunger. Eating Disorders Examination-Bariatric Surgery Version135: Identical to the widely-used Eating Disorders Examination but also measures eating disturbances specific to bariatric surgery by adding specific questions regarding dumping, plugging, chewing and spitting, and vomiting. (Note. The diagnosis of BED will be established from the SCID interview. The results of the EDE-BSV will be used as a continuous variable in the analyses described below.) Night Eating Questionnaire (NEQ)127: 14-item scale that measures symptoms of night eating and has been used in bariatric populations previously. Yale Food Addictions Scale136: 25-item mixed response scale that is used to identify those who are using high sugar/high fat foods in ways similar to symptoms that are markers of substance use, such as tolerance, withdrawal, and loss of control. A composite measure of disordered eating will be calculated by averaging individual z-scores derived from these measures. We predict that higher levels of disordered eating will be associated with less weight loss 24 months following bariatric surgery. Weight: Weight will be measured with a calibrated digital scale with subjects dressed in light clothing and without shoes. Percent weight loss will be calculated from participants current weight (at each assessment point) as compared to their baseline weight. Participants with higher levels of impulsivity, psychopathology, and disordered eating are predicted to lose less weight at 24 months as compared to those with lower levels. Psychosocial Status: Medical Outcomes Study 36-Item Short Form Survey (SF-36)137: used to measure quality of life Impact of Weight on Quality of Life-Lite (IWOOL-Lite) 138: used to measure quality of life Dietary Intake: ASA-24: public-access, freely available (through the National Cancer Institute), web-based tool to obtain high-quality dietary intake data with minimal bias, making it a preferred tool for studying diet and disease associations.139 These 24-hour food recalls will be conducted at each time point for one weekday and one weekend day. Physical Activity: College Alumnus Survey (commonly known as the Paffenbarger Survey140): calculate self-reported leisure time physical activity kilocaloric expenditure per week. The frame of reference will be the past 6

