
The following documents are currently attached to this item:

There are no documents attached for this item.

Deception

Does your project use deception? No

Analysis Plan

Analysis will be conducted using Stata 13.0 (Stata Corporation, College Station, TX). After the completion of quality assurance procedures, descriptive statistics will be summarized for all patients by predictor group (dichotomized). Data screening: Prior to performing analyses, standard data screening/ cleaning procedures will be applied. These procedures will: screen the data for data-entry errors; check for outliers; assess the extent and pattern of missing data; create all summary scores needed for analysis; and check that appropriate assumptions of normality are met. In all analyses, the assumptions underlying the application of all the statistical methods that are used will be examined, principally through the use of standardized residuals, influence diagnostics, and graphical displays. Image processing will include image quality assessment procedures that examine global and region of interest (ROI) based raw and processed temporal signal-to-noise ratio, absolute and relative motion, and signal spike count. Potential outliers will be identified in the cumulative sample by examining quality assessment measures and flagging for further investigation subjects greater than two standard deviations from the mean on any one measure (i.e., behavioral performance, image distortion and artifact, general linear model fit). The purpose of this evaluation is to determine whether the time series is likely valid, and, if so, it will remain. Otherwise it will be corrected, if feasible, or removed from the analysis. The final sample will be examined in a similar fashion to determine whether any subjects warrant data cleaning or require exclusion from the final statistical analysis. Analysis of repeated measures: Our four-session within-subject design will generate multiple outcome measures that belong to the Gaussian family, and we will therefore use standard repeated-measures analysis of variance (ANOVA). Imaging outcomes (perfusion and BOLD) will be modeled using standard voxel-based image analysis techniques (described below) that incorporate random effects. Other outcomes (weight loss, ratings) will be modeled using a linear mixed-effects models framework, using using Stata 13.0 (Stata Corporation, College Station, TX). We could use a population averaged approach such as generalized estimating equations. However, the mixed model approach will provide the flexibility to allow for different error variances for different sessions if necessary. Voxel-based image analysis has limited flexibility, particularly when adding multiple covariates and interaction. When needed, summary values (e.g., mean rCBF, mean BOLD% signal change) extracted from ROIs will be modeled in STATAs mixed-models framework. These models can be extended to include additional explanatory variables (e.g., weight change, heart rate, respirations, age). Primary Aim 1 We will take a mixed models approach. The main interest in this study is the Group x Time interaction, where Group will be a between-subjects factor and Time will be a categorical within-subjects factor. This can be interpreted as population averages (GEE fitting method). Hypothesis 1: We will fit a 2 (Group: Dichotomized Baseline Measures, Low, High) x 3 (Time: change from baseline to month 6, 12 and 24) mixed-effects model for change in weight. Hypothesis 2: We will fit a 2 (Group: Dichotomized difference scores, 6 Month minus Baseline, Low, High) x 2 (Time: change from baseline to months 12 and 24) mixedeffects model for change in weight. In addition, the mixed effects models will include adjustments for surgical procedure, gender, and time since surgery. We recognize that the change in weight could also be associated with effects of several pertinent patient characteristics. To this end, we will consider additional covariates (e.g. sociodemographic variables, comorbidities, medication use, tobacco use, and initial weight). For both hypotheses, we will explore the continuous version of our predictor variables, where in place of Group, we use the real values of the predictor. This yields a difference of slopes with respect to predictor value across time points. Secondary Aim 1 We will use confirmatory factor analysis to verify our expected natural groupings of individual measures into composite measures. We will specify 3 factors and use Varimax rotation. We will assemble composite scores for each of our constructs by summing the standardized score values. We will then standardize the composite score and outcome (change in weight at 24 months). We will estimate the partial correlations (direct and indirect) among individual measures, composites, and outcome in a path analysis as suggested by Figure 1 to estimate the fraction of variance in outcome accounted for by each of the constructs. Secondary Aim 2 The outcomes will consist of (continuous) changes in behavior from baseline. We will use correlation to examine the relationship of baseline impulsivity measures to changes at 6, 12 and 24 months. The exception is changes in diet composition. In this analysis, we will use multivariate regression methods,

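### The fixed Aim 1 covariates omit recruiting site and leave initial weight optional, and two of the optional covariates can duplicate some predictors

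*Combined protocol and SAP*

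**What the plan says.** Under Primary Aim 1 of the Analysis Plan, "the mixed effects models will include adjustments for surgical procedure, gender, and time since surgery". The next sentences add an open list: "we will consider additional covariates (e.g. sociodemographic variables, comorbidities, medication use, tobacco use, and initial weight". No rule says which of these enter, when, or for which predictor. Recruiting site appears in neither list.

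The same section states the contrast: "The main interest in this study is the Group x Time interaction". The outcome there is called only change in weight. The one weight-loss measure that is defined is in the Procedures section: "Percent weight loss will be calculated from participants current weight (at each assessment point) as compared to their baseline weight".

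Other sections bear on the choice of covariates:

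- **Background.** One literature review "concluded that the preoperative factors of BMI, BED, and the presence of personality disorders provided the strongest negative associations with postoperative weight loss".
- **Accrual.** "In order to increase the diversity and size of our sample, participants will also be recruited from the Temple Health Bariatric Surgery Program". The Subject recruitment section adds that Spanish-language forms are offered at Temple only.
- **Procedures, psychopathology measures.** These include a nicotine questionnaire, described as a "self-report designed to measure physical dependence to nicotine", and the psychopathology composite takes in the substance use measures.
- **Subject recruitment.** Psychiatric medications are collected from charts along with psychological diagnoses.

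**The concern.** There is no randomisation. The groups are patients high or low on a psychological or behavioural measure, so anything related to both that measure and weight loss can create or hide an association. The protocol itself points to two such variables. Preoperative BMI is named as a leading correlate of the outcome. Site can differ in patient mix and also in how the predictors are measured, because one programme offers the instruments in two languages. Neither is in the set that every model must contain.

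The Missing data section relies on dropout being explained by observed variables. A mixed model gives that protection only for variables that are in it, so omitting site or weight weakens the defence if either is related to dropout.

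The optional list has the opposite problem for some predictors. Adjusting a nicotine-dependence predictor for tobacco use removes part of the association the model is meant to estimate.

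**Working it through.** The plan gives no figure on this point to reproduce. The text available states no alpha, power, effect size or standard deviation; parts of the document were removed, so I do not count that as a fault.

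Inputs from the documents: 300 patients with a completed baseline visit and two programmes (Accrual); three follow-up times for Hypothesis 1 and two for Hypothesis 2 (Analysis Plan). My assumptions: correlations of 0.1 to 0.3, two-sided 5% tests, 80% power, a median split and no true effect.

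**1. Where each variable stands**

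| Variable | Fixed set | Optional list | Note |
|---|---|---|---|
| Procedure, gender, time since surgery | yes | – | – |
| Initial weight | no | yes | measured at baseline |
| Recruiting site | no | no | known at recruitment |
| Tobacco use | no | yes | nicotine questionnaire is itself a predictor |
| Medication use | no | yes, undefined | may or may not include psychiatric drugs |

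**2. Precision on the percent scale.** If initial weight correlates r with percent loss, adjusting is worth 1/(1 − r²) − 1 in sample size:

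- r = 0.1: 1/0.99 − 1 = 1.0%
- r = 0.2: 1/0.96 − 1 = 4.2%
- r = 0.3: 1/0.91 − 1 = 9.9%

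**3. Confounding, illustration only.** Let r1 be the correlation of the predictor with initial weight, and r2 that of initial weight with the outcome. With a median split, omitting initial weight gives a spurious standardised difference d = 1.596 × r1 × r2, with standard error √(4/300) = 0.115 for a single between-group comparison:

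- r1 = r2 = 0.1: d = 0.016, type I error 0.052
- r1 = r2 = 0.2: d = 0.064, type I error 0.086
- r1 = r2 = 0.3: d = 0.144, type I error 0.238

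For scale, the detectable difference is (1.960 + 0.842) × 0.1155 = 0.32. The documents give neither r1 nor r2.

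**4. Which terms an added covariate moves.** Initial weight and site are constant within a patient. As main effects they cancel from any difference between two visits, so in complete balanced data they cannot change Group x Time. One simulated data set (300 patients, no group effect, weight effect growing over three visits) shows this. It shows which terms move, not by how much in this study.

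| Model | Group | Group x Time (2nd, 3rd visit) | Last-visit contrast |
|---|---|---|---|
| No weight | −0.055 | −0.042, 0.072 | −0.055 + 0.072 = 0.017 |
| Weight, main effect | −0.138 | −0.042, 0.072 | −0.138 + 0.072 = −0.066 |
| Weight and weight x time | −0.089 | −0.088, −0.027 | −0.089 − 0.027 = −0.116 |

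The main effect moves the last-visit contrast but not the interaction. The by-time term moves both.

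**5. Overlap.** Adjusting for a covariate correlated ρ with the predictor multiplies the variance by 1/(1 − ρ²). For assumed ρ of 0.3, 0.5 and 0.7 this is 1.10, 1.33 and 1.96, an effective 273, 225 and 153 of 300 patients. The quantity being estimated also changes.

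**The case against.** The best counter-argument is that initial weight is not ignored: it is named as a candidate, and percent loss already scales by it. Forcing it in may also be wrong. The Background argues that poor impulse control and disinhibition contribute to the development of extreme obesity, so initial weight may lie partly downstream of the predictors, and adjusting for it could remove part of their effect. This stands, and is why a model without baseline weight should be reported too. It does not apply to site.

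It is also fair that main-effect adjustment would leave the stated contrast untouched. That shapes the remedy but does not remove the need for it. The Objectives predict smaller losses at two years, a contrast that does move, and incomplete data are expected.

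Several stronger readings are tempting, but the documents do not support them:

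- **A large precision gain.** Thinking in kilograms, a reader might infer a gain of 19% to 48% (assuming 125 ± 22 kg, mean percent loss 28, SD 7 to 11). That needs percent loss to be independent of initial weight, which conflicts with the negative BMI association in the Background. Assumed correlations of −0.1 to −0.3 bring it to 2% to 36%. The defined measure is percent of baseline in any case.
- **Psychiatric drugs as a stated covariate.** Medication use is not defined. Elsewhere the protocol speaks of antidiabetes and antihypertensive drugs, so this overlap is conditional.
- **Tobacco as over-adjustment in every psychopathology model.** Aim 1 uses individual measures. For a depression score, or for impulsivity or eating measures, tobacco may be a proper confounder.
- **Temple as a deliberately different population.** The stated reasons are diversity and size, and patient flow is described as similar.
- **Covariates chosen on results.** Five optional classes allow 2⁵ = 32 models, and taking the best p-value raised simulated type I error from 0.048 to 0.097. The plan gives no selection rule, but it does not propose that practice.

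**Conclusion.** The point holds as an omission in the adjustment set that should be corrected before analysis. Site is missing altogether, and initial weight is discretionary despite the protocol's own account of BMI as a leading correlate. The overlap problem is narrower: it is direct for tobacco with nicotine-related predictors, and conditional for medication use.

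The precision gain is about 1% to 10%, and that rests on assumed correlations of 0.1 to 0.3. A reader might infer that the Aim 1 results will be materially biased. The documents do not show it: the illustrated type I error runs from a negligible 0.052 to a serious 0.238 depending wholly on assumed correlations, it refers to a single between-group comparison rather than Group x Time, and no site split is given. The case rests on two variables with a documented reason to matter, both already available, in an observational comparison.

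**What to change.** Amend Primary Aim 1 of the Analysis Plan as follows:

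1. Add site (Penn or Temple) and baseline weight to the fixed covariates for both hypotheses, each with a covariate-by-time term. Alternatively, name the month-24 group contrast as the test.
2. Report a sensitivity analysis without baseline weight, giving the reason that it may lie partly downstream of impulsivity or disordered eating.
3. Do not adjust for tobacco use where the predictor is the nicotine questionnaire, a tobacco-related diagnosis, or a composite containing either.
4. Define medication use. If it includes psychiatric drugs, leave those out of models whose predictor is a psychiatric diagnosis or symptom measure.

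The cost is wording and a few degrees of freedom. With by-time terms, two covariates take 2 × 3 = 6 parameters under Hypothesis 1 and 2 × 2 = 4 under Hypothesis 2, in about 300 patients. No new data are needed.
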